1.2.1 Prior Experience of Tilmanocept Injection in KS Patients

Imaging of KS with high specificity and sensitivity has been a remarkable challenge even with today's high resolution technology and available imaging agents⁽¹⁷⁻²⁹⁾. In addition to the ex vivo study, [name] completed a phase II clinical pilot study in KS patients at the University of California San Francisco (UCSF Protocol 14-13522). Five subjects received a subcutaneous injection of 50 µg tilmanocept radiolabeled with 2.0 mCi Tc 99m. No subjects experienced any SAEs. Three AEs were reported in two subjects, including peripheral edema (probably not related to study drug or procedures) and fatigue and nausea (possibly related to study drug or procedures). No interaction of tilmanocept with HAART therapy or other drugs utilized in the treatment of HIV or HHV8 was observed.

Tc 99m tilmanocept localized regionally in clinically confirmed KS lesions as well as lymph nodes, as shown in [Figure 4](#). Thus, this receptor targeting approach to CD206 presents itself as a novel portal for imaging and staging KS. Based on this previous experience, it is anticipated that IV-administered Tc 99m tilmanocept will be able to systemically localize both cutaneous and non-cutaneous (i.e. visceral or CNS) KS lesions.

Figure 4. Localization of Tc 99m Tilmanocept in KS Lesions

1.3 Previous Experience with Tc 99m Tilmanocept

A detailed evaluation of safety and efficacy data from nonclinical and clinical studies can be found in the accompanying Investigator's Brochure supplied by Navidea Biopharmaceuticals, Inc.

1.3.1 Nonclinical Evaluations – IV and Intraperitoneal Administration

Nonclinical studies with tilmanocept demonstrated that the drug selectively binds to its intended receptor (the MBR), is appropriately distributed for radio detection of lymphatic tissue, and is well tolerated by rats, rabbits, guinea pigs, and dogs.

PK (pharmacokinetics) data obtained from SC repeated dose toxicity studies in rats and dogs demonstrated that absorption into the plasma was rapid in both species. Urinary excretion was a major pathway of elimination. A tissue distribution study demonstrated that tilmanocept exhibited rapid clearance from the injection site, rapid uptake by the local lymph node, and low uptake by the remaining lymph nodes. In addition, substantial accumulation was noted in the kidneys, bladder, and bladder contents by 3 hours post dose, providing additional evidence that urinary excretion occurs rapidly and is a major route of elimination. Tilmanocept was well tolerated at all doses tested in nonclinical safety pharmacology studies and in a number of single and repeated dose toxicology studies in rats, rabbits, and dogs. In some studies in rabbits and dogs, tilmanocept acted as a local irritant of the subcutis or skeletal muscle, and induced mild inflammation and tissue degeneration. The no-observed adverse-effect level (NOAEL) in the definitive repeated dose studies in rats and dogs was 42 μ g/kg/day.

Tilmanocept was not mutagenic or genotoxic in vitro (mouse lymphoma test, Ames test) or in vivo (mouse micronucleus test). No signs or symptoms of hypersensitivity were observed in an in vivo study

in male guinea pigs. Most of the nonclinical safety studies used SC drug administration, a proposed route for administration to humans. The human dose for clinical studies is 50 µg Tilmanocept per procedure, equivalent to 0.714 µg/kg if a conservative estimate of 70 kg is used for human body weight. The single dose administration in animals ranged from 14 to 280 µg/kg in animals, which is approximately 20 to 390 times the human µg/kg dose. Repeated doses in animals ranged from 10.5 to 42 µg/kg/day in animals and are approximately 15 and 60 times the human µg/kg dose. These doses were all well tolerated in the nonclinical studies.

Dosing in Dogs, Guinea Pigs and Mice: Intravenous (IV) dosing nonclinical studies represents cumulative dosing in male and female beagle dogs [eight dogs (4/sex; wt females= 7.6 kg; wt males = 10.5 kg) given an IV injection of saline on Study Day (SD) 1 and 2 and DTPA-mannosyl-dextran at 0.084 mg/kg on SD 4, 0.42 mg/kg on SD 6, and 0.84 mg/kg on SD 8 and 10] 1,560X the 50 µg and 195X the 400 µg dose (female dogs) and 1706X the 50 µg dose and 213X the 400µg dose (male dogs). Based on the highest single dose administration (0.84 mg/kg) the dogs received 600X the 50 µg and 75X the 400 µg dose (female dogs) and 657X the 50 µg and 82X the 400 µg dose (male dogs). [NOTE: In a separate dog study the dose was 0.56 mg/kg in 2 each male and female dogs of similar weight/sex), no effect was noted in that study, consistent with the higher dose dog study].

With regard to the sensitization test (IV administration in guinea pigs, wt = 0.415 kg) the maximum dose was the equivalent of 96X of the anticipated high dose tilmanocept.

Lastly, although intraperitoneal administered in mice, based on the highest single dose administration (2000 mg/kg) the mice received 300,000 X the 50 µg and 37,500X the 400 µg dose (female mice, wt = 22 gm) and 340,000X the 50 µg and 42,500X the 400 µg dose (male mice, wt = 29 gm).

Type of Study / Description	Test System	Method of Administration	Dosing
Central nervous system safety pharmacology	Rat	Intravenous	37, 190, and 380 µg/animal or equivalent 490X and 61X the anticipated study doses of 50 µg and 400 µg in humans
Expanded single-dose toxicology (including toxicokinetics and local tolerance)	Rat	Intravenous	37, 190, and 380 µg/animal or equivalent 490X and 61X the anticipated study doses of 50 µg and 400 µg in humans
Respiratory Safety Pharmacology Evaluation Using Head-Out Plethysmography of Tilmanocept following Intravenous Bolus Injection in Male Rats	Rat	Intravenous	60, 120, and 300 µg/animal or equivalent 320X and 41X the anticipated study doses of 50 µg and 400 µg in humans
In Vitro Evaluation of Tilmanocept as an Inhibitor of Cytochrome P450 (CYP) Enzymes in Human Liver Microsomes	Human Liver Samples	In vitro	0.6 to 600 nM

Type of Study / Description	Test System	Method of Administration	Dosing
In Vitro Evaluation of Tilmanocept as an Inhibitor of Human ABC and SLC Transporters	Human Liver Samples	In vitro	0.04, 0.4 μ M
Pharmacokinetics, Excretion, and Distribution by Quantitative Whole-Body Autoradiography Following Intravenous Administration of 99mTc-Tilmanocept in Rats	Rat	Intravenous	25 μ g in 0.5 mL with collection of Blood, Urine, Feces, and Carcasses for QWBA
Hemolysis and protein flocculation	Human blood samples	In vitro	2.5, 25, and 250 μ g/mL whole human blood
Target profiling screen	Ion Channel	In vitro	See Individual Tests Below
K Ion Channel	Ion Channel	The cardiac potassium channel, hERG, is responsible for a rapid delayed rectifier current (IKr) in human ventricles. This channel has been selected for evaluation because inhibition of IKr is the most common cause of cardiac action potential prolongation by non-cardiac drugs. In this assay, hERG potassium channels are expressed in a human embryonic kidney (HEK293) cell line that lacks endogenous IKr.	0.025, 0.05, 0.25, 0.5 mg/mL
Na Ion Channel	Ion Channel	Cloned hNav1.5 sodium channels (SCN5A gene expressed in CHO cells)	0.025, 0.05, 0.25, 0.5 mg/mL

Type of Study / Description	Test System	Method of Administration	Dosing
Ca Ion Channel	Ion Channel	1. Cloned L-type calcium channels (hCav1.2, encoded by the human CACNA1C gene and coexpressed with the β 2 subunit, encoded by the human CACNB2 gene and the α 2 δ 1 subunit encoded by the human CACNA2D1 gene in CHO cells), responsible for ICa,L, high threshold calcium current. 2. Cloned hNav1.5 sodium channels (SCN5A gene expressed in CHO cells).	0.025-0.5 mg/mL

Conclusions from these Tests:

CNS: In conclusion, a single IV administration of tilmanocept was well tolerated in rats at levels of 0.15, 0.75, and 1.50 mg/kg. Brief sedation shortly after dosing was observed at 0.75 and 1.50 mg/kg, which resolved by the time of the first functional observational battery assessments and was attributed to the mannosyl-dextran content of tilmanocept. There were no tilmanocept-related effects on functional observational battery parameters.

Single Bolus Toxicity: Tilmanocept-related clinical pathology changes were limited to minimally greater, dose-related, aspartate aminotransferase values for 0.75 and 1.5 mg/kg males and females that were likely caused by muscle or erythrocyte release as changes did not occur in other hepatobiliary-related clinical pathology parameters. This change had resolved at the end of the recovery phase.

At the Day 2 necropsy, dark focus in the glandular stomach was considered to be a potential test article-related gross pathology finding in males at \geq 0.75 mg/kg. The gross finding of dark focus in the stomach correlated microscopically with focal erosion or minimal hemorrhage. Focal erosion in the stomach was test article related in males at \geq 0.75 mg/kg, but was considered to be of little toxicological significance. No test article-related organ weight changes were noted. At the end of the recovery phase (Day 15), there were no test article-related findings in gross pathology, organ weights, or histopathology.

Respiratory: In conclusion, respiratory function was assessed in male Crl:CD(SD) rats given a single IV injection dose of vehicle control article or 0.150, 0.300, or 0.750 mg/kg of tilmanocept at a dose volume of 3 mL/kg. Administration of tilmanocept had no effect on mortality, but it was associated with severe abnormal clinical observations of hypoactivity, ataxia, labored or irregular respiration, and pale skin of entire body for animals given 0.750 mg/kg. Administration of >0.150 mg/kg tilmanocept had no direct effect on respiration rate, but it was associated with higher tidal volume (up to +26, +14, and +50% in animals given 0.150, 0.300, or 0.750 mg/kg, respectively) and higher minute volume (up to +18, +5, and +40% 0.5 through 1 hour post-dose in animals given 0.150, 0.300, or 0.750 mg/kg, respectively).

CYP: This study was designed to independently evaluate the in vitro inhibitory effect of tilmanocept on major CYP enzymes in human liver microsomes. Specifically, the inhibition of CYP1A2, CYP2B6, CYP2C8, CYP2C9, CYP2C19, CYP2D6 and CYP3A4/5 (utilizing two different substrates) by tilmanocept was assessed with the aim of ascertaining the potential of tilmanocept to inhibit the metabolism of concomitantly administered drugs.

To evaluate tilmanocept as a direct, time-dependent and metabolism-dependent inhibitor of CYP activity, human liver microsomes from a pool of 200 human donor sources were incubated with marker substrates in the presence or absence of tilmanocept. To distinguish between time-dependent and metabolism-dependent inhibition, tilmanocept was preincubated with human liver microsomes for 30 min without and with an NADPH-generating system, respectively, prior to the incubation with the marker substrate. Known direct and metabolism-dependent inhibitors of CYP enzymes were included as positive controls in all experiments.

Under these experimental conditions, there was little or no evidence of direct, time- or metabolism-dependent inhibition of any CYP enzyme by tilmanocept.

ABC and SLC transporters: It was found that tilmanocept was not an inhibitor of human transporters (namely P-gp, BRCP, OAT1B1, OATP1B3, OAT1, OAT3, and OCT2) under the conditions tested.

Hemolysis: No hemolysis and no flocculation were observed following in vitro treatment of human whole blood with tilmanocept at final whole blood concentrations of 2.5, 25 or 250 µg/mL.

Ion Channels (Na⁺, K⁺, Ca²⁺): Although there is a small dose-dependent effect that is fractional to the positive control, variability within concentration renders the median value observations not significantly different (Kruskal-Wallis).

1.3.2 Clinical Pharmacokinetics and Pharmacodynamics in Lymphatic Mapping Clinical Trials (Subcutaneous, Peritumoral and Intradermal administration)

After a single peritumoral (PT), ID, or SC dose for solid tumor lymphatic mapping, Tc 99m tilmanocept demonstrated significantly faster injection site clearance than Tc 99m sulfur colloid (TcSC, filtered and unfiltered), the standard imaging agent and comparator used in the Phase 1 trials.

The mean Tc 99m tilmanocept injection site clearance half-life was approximately 2 to 3 hours vs. approximately 15 to 27 hours for TcSC. Absolute uptake in the primary “sentinel” lymph node (L_{SN}) was dose-related for Tilmanocept, although relative nodal uptake (%ID_{SN}) overall was independent of dose and ranged from 0.05%ID_{SN} to 1.81%ID_{SN}, while the TcSC values ranged from 0.64%ID_{SN} to 3.66%ID_{SN}; differences between Tc 99m tilmanocept and TcSC were not statistically significant.

In the Phase 2 trial, Tc 99m tilmanocept was highly effective in identifying tumor-draining lymph nodes (i.e., overall, a “hot spot” from Tc 99m tilmanocept was identified in 93.0% of patients for whom preoperative lymphoscintigraphy was performed, and the per patient intraoperative localization rate was 96.2%). Diagnostic performance of in vivo Tc 99m tilmanocept findings relative to pathology assessment of tumor tissue indicated a high per tissue sensitivity estimate (overall, 92.0%). The overall false negative rate (FNR) for pathology was 8.0%, supporting the accuracy of Tc 99m tilmanocept in identifying lymph nodes with a high potential for containing tumor metastases in the lymphatics draining the tumor bed. The effect of time between Tc 99m tilmanocept injection and surgery on the localization rate was also evaluated, with surgeries done either on the same day as the Tc 99m tilmanocept injection or on the following day. In patients with melanoma, the time interval made no difference in the localization rate. In patients with breast cancer, the same day surgery group had a

95.5% (21 out of 22 patients) localization rate compared with 88.9% (8 of 9 patients) in the next-day surgery group, although the difference is not statistically significant ($p = 0.5032$, Fisher's exact test) and can be attributed to the small number of breast cancer patients in the next day surgery group, and not the time between injection and surgery.

1.3.3 Clinical Efficacy in Lymphatic Mapping/Sentinel Node Mapping Clinical Trials

Clinical efficacy was evaluated in two pivotal Phase 3 clinical trials in patients with breast cancer and melanoma, comparing lymph node detection of Tc 99m tilmanocept and with the FDA-approved intraoperative Tc 99m tilmanocept mapping (ILM) agent and standard-of-care, vital blue dye (VBD). Tc 99m tilmanocept demonstrated a statistically significant concordance rate with VBD (meta-analysis concordance rate = 99.99%, $p < 0.0001$).

The detection concordance between Tc 99m tilmanocept and VBD was similar among patients with melanoma and patients with breast cancer (meta-analysis concordance rate = 99.99% for both populations). Tc 99m tilmanocept also demonstrated a higher sensitivity for detecting tumor-positive (as confirmed by pathology) lymph nodes, corresponding to a decreased FNR when compared with VBD on a per node basis. The corresponding sensitivity rate in detection of lymph nodes most likely to be positive for tumor cells for Tc 99m tilmanocept was 99.99%, compared with 78.02% for VBD. The FNR for VBD (21.98%) was higher than the FNR for Tc 99m tilmanocept (0.01%). These findings suggest that, when VBD is used as the imaging agent, there is an increased risk of missing the detection of tumor-involved lymph nodes and incorrectly staging cancer patients. The Tc 99m tilmanocept-only findings (pathology-positive nodes that were hot/not blue) suggest that Tc 99m tilmanocept was markedly more effective in identifying lymph nodes that harbored disease than was VBD. Clinical safety has been evaluated in an integrated analysis of the pooled safety population (506 patients) from six completed trials and one ongoing clinical trial. No on-study deaths in Tc 99m tilmanocept -treated patients have occurred in this population. Twenty-seven serious adverse events (SAEs) have been reported for 26 patients across all Tilmanocept studies. None of the SAEs were attributed to the use of Tc 99m tilmanocept. No patients were withdrawn from any study due to an SAE or adverse event (AE). No clinically significant safety event associated with the use of Tc 99m tilmanocept has been reported in the clinical trials.

1.3.4 Clinical Safety using Intradermal, Subcutaneous, Peritumoral, and Intravenous Injections

Non-IV Experience - Well over 250,000 patients in clinical trials and US commercial use for intraoperative lymphatic mapping (ILM) with sentinel lymph node biopsy (SLNB) have been exposed to tilmanocept, and there have been no safety signals, no deaths due to drug, and no SAEs due to tilmanocept. There are no known drug interactions leading to contraindications with the use of tilmanocept. Post-marketing reports have shown less than 0.12% of subjects experiencing AEs, with the most common one being lack of node localization.

IV Experience - Navidea is currently conducting disease imaging studies in patients with rheumatoid arthritis (RA), nonalcoholic steatohepatitis (NASH), colorectal cancer (CRC) with metastases to the liver, and cardiovascular disease (CVD) utilizing Tc 99m tilmanocept administered IV. Dosages consist of 50, 100, 200 or 400 μ g of tilmanocept labeled with 1, 2, 5, or 10 millicurie(s) (mCi) of ^{99m}Tc injected IV. At the time of this writing, sixty (60) subjects have received IV administration of Tc 99m tilmanocept. No subject has exhibited any adverse reaction to the drug that was related to the drug.

2 TRIAL OBJECTIVES

2.1 Primary Objective(s)

To determine the safety of escalating IV doses of Tc 99m tilmanocept in HIV subjects with biopsy-confirmed KS.

2.2 Secondary Objective(s)

- Concordance between clinical assessment/diagnosis and the localization of Tc 99m tilmanocept by planar and/or SPECT/CT imaging in cutaneous and non-cutaneous sites of KS.
- Qualify and quantify Tc 99m tilmanocept localization intensity on imaging with CD206 locale and quantity by histology and IHC in biopsied KS lesions to determine optimal IV dose.
- Concordance of localization of Tc 99m tilmanocept via IV and SC routes of administration by planar and/or SPECT/CT imaging in cutaneous and non-cutaneous sites of KS.

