8.4 Post-Injection and Imaging Biopsy Acquisition

The purpose of the KS lesion biopsy will be to determine the proportion of CD206-expressing cells and quantity of CD206 (IHC fluorescence) in KS tissues in parallel with an analysis of KS imaged with Tc 99m tilmanocept. A non-visceral site of KS for biopsy post-imaging in each subject will be chosen by the Nuclear Medicine physician based on visualized localization and lesion size. If no lesion is determined to localize Tc 99m tilmanocept, a lesion of at least 5-6 mm in a clinically accessible area will be biopsied as chosen by the Investigator(s) who will record selection and rationale.

All subjects will receive the biopsy on the day of IV Tc 99m tilmanocept administration at the completion of imaging.

A biopsy up to 6mm of the designated lesion will be taken, and a photograph of the biopsy site with a measurement scale will be taken and stored with the subject's research chart. The tissue will be obtained at the completion of Tc 99m tilmanocept IV injection and imaging and delivered on ice to the Department of Pathology at Zuckerberg San Francisco General Hospital. The biopsy will be sectioned into a formalin-fixed paraffin-embedded (FFPE) segment and a fresh or frozen segment to be used for other analyses. FFPE tissue sections will be quantified for CD206 and LANA through a standardized quantitative image analysis program. HHV8 will be quantified by qPCR.

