9.5.3 Analysis of Efficacy Variables

The number and percentage of subjects with at least one biopsy-confirmed or clinically suspected KS lesion that has localized with Tc 99m tilmanocept by planar and/or SPECT/CT imaging will be

computed. A 95% exact confidence interval on the per subject localization rate will be computed. This analysis will be performed by dose.

Per region lesion localization of Tc 99m tilmanocept by planar and/or SPECT/CT imaging will be computed across all biopsy-confirmed or clinically suspected KS lesions of all subjects. A 95% exact confidence interval on per region lesion localization will be calculated. This analysis will be performed by dose.

Localization intensities of biopsied lesions will be summarized by descriptive statistics (mean, median, standard deviation, minimum, maximum and range) for each dose.

Per biopsied lesion proportion of CD206-expressing cells and quantity of CD206 as determined by histology and IHC fluorescence will be summarized by descriptive statistics (mean, median, standard deviation, minimum, maximum and range) for each dose.

Concordance between between IV and SC tilmanocept in biopsy-confirmed or clinically suspected KS lesion sites will be assessed with a cross-tabulation including the joint probability distribution. The site will be the sampling unit for this analysis. An exact version of McNemar's test will be performed, testing the null hypothesis

$$H_0: \pi_{IV} = \pi_{SC}$$

$$H_A: \pi_{IV} \neq \pi_{SC}$$

where π_{IV} and π_{SC} represent the probabilities of localization with IV (only) tilmanocept and localization with SC tilmanocept only respectively.

In addition, descriptive statistics will be generated relative to the concordance and reverse concordance of observed sites of discrete localization of Tc 99m tilmanocept following IV and SC administration.

The number and percentage of subjects with at least one anatomical site other than KS that has been localized with Tc 99m tilmanocept by SPECT imaging will be computed. A 95% exact confidence interval on the per subject localization rate will be computed. This analysis will be performed by dose and overall.

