Locations showing localization of Tc 99m tilmanocept by planar and/or SPECT/CT imaging that are not locations of biopsy-confirmed or clinically suspected KS sites will be computed across all sites in all subjects. A 95% exact confidence interval on per location localization will be calculated. This analysis will be performed by dose and overall.

Other efficacy analyses will be described in the Statistical Analysis Plan (SAP) for the study.

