2.0 Data Analysis Considerations

2.1 Types of Analyses

All results will be based on descriptive statistics. Unless otherwise stated, continuous variables will be summarized via sample size, mean, standard deviation, median, minimum, and maximum. Categorical variables will be summarized via frequency counts and percentages.

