4.2 Analysis of Efficacy Variables

Localization in KS Sites

The number and percentage of subjects with at least one biopsy-confirmed or clinically suspected KS lesion that has localized with Tc 99m tilmanocept by planar and/or SPECT/CT imaging will be computed. A 95% exact confidence interval on the per-subject localization rate will be computed. This analysis will be performed by dose group and route of administration.

Per-lesion/region localization of Tc 99m tilmanocept by planar and/or SPECT/CT imaging will be computed across all biopsy-confirmed or clinically suspected KS lesions of all subjects. A 95% exact confidence interval on the per-lesion/region localization will be calculated. This analysis will be performed by dose group and route of administration.

An analysis table will also be provided to display the counts of KS lesions localized by imaging that were not previously identified clinically.

Concordance between IV and SC tilmanocept in biopsy-confirmed or clinically-suspected KS lesion sites will be assessed with a cross-tabulation of the IV and SC findings, including the joint probability distribution. The sampling unit for this analysis will be the site. An exact conditional version of McNemar's test will be performed to test the hypotheses

$$H_0: \pi_{IV} = \pi_{SC}$$
$$H_A: \pi_{IV} \neq \pi_{SC},$$

where π_{IV} and π_{SC} represent the probabilities of localization with IV (only) tilmanocept and SC (only) tilmanocept, respectively. In addition, the number and proportion of subjects with concordance and reverse concordance of observed sites of discrete localization of Tc 99m tilmanocept following IV and SC localization will be summarized.

Localization Intensity by Planar and/or SPECT/CT Imaging

Tc 99m tilmanocept average pixel intensity and percent above background will be summarized with descriptive statistics (mean, standard deviation, minimum, median, maximum, and range) for each biopsied lesion localized on imaging following IV injection of Tc 99m tilmanocept by dose group. Summary statistics will be presented separately by imaging type (planar, SPECT/CT).

Proportion of CD206-expressing Cells

Per biopsied-lesion proportion of CD206-expressing cells as determined by histology and IHC fluorescence will be summarized by descriptive statistics (mean, standard deviation, minimum, median, maximum, and range) by dose group.

Localization in Non-KS Sites

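### No planned output pairs imaging intensity with CD206 in the same biopsied lesion, although secondary objective 2 sets the two together

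*Protocol*

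**What the plan says.** The objective is in Protocol 2.2 and is repeated in SAP 1.0 and 4.1: "Qualify and quantify Tc 99m tilmanocept localization intensity on imaging with CD206 locale and quantity by histology and IHC in biopsied KS lesions". It ends with the determination of the optimal IV dose.

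Protocol 8.4 has every subject biopsied on the day of the IV injection, once imaging is complete. The nuclear medicine physician picks a non-visceral lesion by visualized localization and size; if none localizes, the investigator picks an accessible one. The stated purpose is to obtain the proportion of CD206-expressing cells and the "quantity of CD206 (IHC fluorescence) in KS tissues in parallel with an analysis of KS imaged with Tc 99m tilmanocept".

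The analyses are then specified one quantity at a time:

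- Protocol 9.5.3, on imaging: "Localization intensities of biopsied lesions will be summarized by descriptive statistics", for each dose.
- Protocol 9.5.3, on tissue: "Per biopsied lesion proportion of CD206-expressing cells and quantity of CD206 as determined by histology and IHC fluorescence will be summarized by descriptive statistics", again for each dose. The section closes with "Other efficacy analyses will be described in the Statistical Analysis Plan (SAP) for the study".
- SAP 4.2 keeps two separate headings. Average pixel intensity and percent above background are summarised by dose group and imaging type, for biopsied lesions localized after IV injection. For tissue, "Per biopsied-lesion proportion of CD206-expressing cells as determined by histology and IHC fluorescence will be summarized by descriptive statistics", by dose group.
- SAP 2.1 sets the general approach: "All results will be based on descriptive statistics".

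**The concern.** The objective names intensity and CD206 together in biopsied lesions, and the design yields both for one lesion in each subject on the same day. The natural question is whether lesions that take up more tracer carry more CD206. Separate summaries by cohort cannot show this, because they discard which intensity belongs to which CD206 value.

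The protocol leaves further efficacy analyses to the SAP, and the SAP does not add the joint one. If it is improvised after the data are seen, the choice of imaging type, intensity measure, CD206 measure and handling of non-localized lesions is all open. With so few pairs, each of those choices could change the result.

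**Working it through.** **1. What each planned output holds.**

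| Output | Intensity | CD206 | Both for one lesion |
|---|---|---|---|
| Protocol 9.5.3 | own paragraph | own paragraph | no |
| SAP 4.2 | own heading | own heading | no |
| SAP Table 10 (planar), Table 11 (SPECT/CT) | yes | no | no |
| SAP Table 12 | no | yes, with HHV8 | no |
| Listing 17 | yes | no | no |
| Listing 19 | no | yes | no |

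The SAP's list of outputs (Section 7.0) contains no figure, correlation or merged listing for these two quantities.

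**2. Which lesions enter.** SAP 4.1 and 4.2 restrict intensity to biopsied lesions localized on imaging. The CD206 summary has no such restriction, and Protocol 8.4 requires a biopsy even when nothing localizes. A subject whose biopsied lesion did not localize therefore counts in Table 12 but not in Tables 10 and 11.

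**3. How many pairs.** The plan's own total reproduces from Protocol Table 1: 4 + 4 + 6 = 14 subjects. With one biopsy per subject, 14 pairs is the ceiling at planned enrolment. The shells for Tables 10-12 have rows for Cohorts 2 and 3 and for all cohorts combined, but none for Cohort 1, although SAP 4.2 says by dose group. If Cohort 1 is left out, the ceiling is 4 + 6 = 10. Non-localized lesions lower it further, and SPECT/CT is optional, so SPECT/CT pairs may be fewer still.

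**4. Separate summaries do not determine the association.** Illustration with four lesions (invented values): intensities 10, 20, 30, 40 and CD206 proportions 0.2, 0.4, 0.6, 0.8. Mean, SD, median, minimum and maximum of each are fixed, yet:

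- CD206 in the order 0.2, 0.4, 0.6, 0.8 gives r = +1
- 0.4, 0.8, 0.2, 0.6 gives r = 0
- 0.8, 0.6, 0.4, 0.2 gives r = -1

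Tables in the format of 10-12 would be identical in all three cases.

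**5. What a paired analysis could deliver.** The documents give no expected correlation or alpha for this objective; the r values and the two-sided 0.05 level are my assumptions. Approximate 95% interval: tanh(atanh(r) ± 1.96/√(n - 3)).

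- n = 14: 1.96/√11 = 0.59. Observed r = 0.5 gives -0.04 to 0.81; r = 0.7 gives 0.27 to 0.90.
- n = 10: 1.96/√7 = 0.74. Observed r = 0.7 gives 0.13 to 0.92.

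This formula is for Pearson's r; an interval for Spearman's coefficient is usually somewhat wider.

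Within a single cohort, the smallest |r| that differs from zero at the 0.05 level is t/√(n - 2 + t²), with t on n - 2 degrees of freedom:

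- n = 4: 4.303/√(2 + 18.51) = 0.95
- n = 6: 2.776/√(4 + 7.71) = 0.81

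Only a pooled estimate is workable, and only as description.

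**The case against.** The objective names no correlation. Objectives 1 and 3 ask for concordance by name; objective 2 does not, and Protocol 8.4 says only that CD206 is measured "in KS tissues in parallel with an analysis of KS imaged with Tc 99m tilmanocept". The endpoint lists in Protocol 9.3 and SAP 4.1 give intensity and CD206 as separate per-lesion endpoints, and both are summarised. The study is a small Phase 1 safety trial with a descriptive SAP. Listings 17 and 19 both carry the subject number, so with one biopsy each the pairs can be matched.

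Much of this stands. The wording is loose enough for a side-by-side reading, and the information is not lost. But no side-by-side display is planned either, and the Listing 17 shell has no column for imaging type, so a match by hand would not show which scan the intensity came from. A scatter plot and a correlation with an interval fit within a descriptive SAP.

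A reader might infer more than the documents support:

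- *That the objective gets no answer at all.* Each quantity is described by dose group with mean, SD, n, range and median, and combined across cohorts. What is missing is the joint view.
- *That pairing would separate a dose effect from chance differences in CD206 between cohorts.* It would not. Cohorts are non-randomised, of 4 to 6 subjects, and the lesions are chosen on visualization. Dividing intensity by CD206 does not remove that problem.
- *That CD206 in the biopsy cannot depend on the cohort because the tissue is taken so soon after injection.* The documents do not say this, and the point does not need it.

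**Conclusion.** The point holds as a gap in the planned displays and statistics for one secondary objective. Intensity and CD206 are available for the same lesion, and nothing planned joins them. In addition, the two summaries can rest on different sets of lesions.

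The size is modest: 14 pairs at most, possibly 10 or fewer, with an interval that would span most of the positive range even for a strong observed correlation. The figure of 14 assumes full planned enrolment, all three cohorts and an intensity value for every biopsied lesion.

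The primary safety endpoint is unaffected. The optimal-dose clause of the objective has no decision rule in either document; a paired analysis would not supply one, and its absence is a separate matter. The change should be made, because without it the planned outputs cannot show whether intensity and CD206 go together.

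**What to change.** Add to SAP 4.2 and to the output list:

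1. One merged per-lesion listing: cohort, subject, lesion, imaging type, average pixel intensity, percent above background, whether the lesion localized, and CD206. Name the CD206 measure: the protocol has both proportion and quantity, while SAP 4.2, Table 12 and Listing 19 carry only the proportion.
2. A scatter plot of planar percent above background against CD206 with cohort marked, and a separate SPECT/CT plot where those scans exist.
3. A pooled Spearman correlation with a 95% confidence interval, labelled descriptive.
4. A rule for non-localized biopsied lesions: measure intensity at the biopsied site for these too, or show them flagged separately.
5. A Cohort 1 row in the shells for Tables 10-12.

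State in the text that there is at most one pair per subject, that the interval will be wide, that lesions were selected on visualization, and that the analysis does not by itself establish an optimal dose. Do not present intensity relative to CD206 as a dose comparison.

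The cost is one listing, one or two figures and one statistic. For localized lesions the data are already planned; measuring intensity at non-localized biopsy sites is the only extra image reading, and flagging those lesions instead avoids it.
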